Early Assisted Discharge for COPD Exacerbations With Telemonitoring.

ClinicalTrials.gov, NCT01951261.

Versión 1. 01/02/2012

**Department Pneumology Hospital Puerta de Hierro and Carlos III Health
Institute.**

**Reseachers: [name], [name], [name], [name].**

Protocol:

The TELEMED-COPD study is a randomized clinical trial with 2 parallel groups (both with early discharge; intervention group: home hospitalization with telemonitoring / control group: traditional follow-up based on face-to-face visits by healthcare personnel). It was carried out at the Puerta de Hierro Hospital from March 2012 to July 2018. Once the informed consent was given by the participants, they were randomly distributed between the two groups using a table of pseudo-randomized numbers in variable blocks generated by computer. The randomization sequence was kept hidden by the randomization system itself. Substitution of patients withdrawn from the study was not performed.

Participation criteria:

Patient admitted with exacerbation of COPD in the Pulmonology Service, with no age limit and who, after an initial phase of clinical stabilization not exceeding 4 days, meets the inclusion criteria: 1) Diagnosis of COPD (prior or during admission according to GOLD 2020), 2) absence of serious decompensated concomitant diseases, 3) arterial blood gas: pH > 7.35, pO₂ > 50 mmHg with O₂ at maximum 3 bpm, Oxygen saturation > 90%, pCO₂ < 55, 4) afebrile more than 48 h, 5) need for administration of maximum bronchodilators every 6 hours, 6) corticosteroids < 40mg / 12 hours, 7) chest radiograph without new onset pathology, 8) subjective improvement, and 9) adequate family environment.

Exclusion criteria: 1) Neoplasms or other end-stage chronic diseases, 2) alcoholism, 3) need for intravenous medication, 4) inability to understand the program and participate in it, 5) have required ICU care or need mechanical ventilation non-invasive during exacerbation, 6) institutionalized patient.

Withdrawal criteria: unsuccessful inability to use telemonitoring, complications derived from hospital admission or at the express request of the patient.

Study variables:

The main variable was the time to the first exacerbation after discharge (exacerbation was defined as an acute and sustained deterioration in the patient's clinical condition, greater than the daily fluctuation and requiring a change in the usual medication)

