The main hypothesis is to verify that after the early discharge, the health results caused by the experimental treatment (intervention) are not inferior to the reference treatment (control). The scientific literature states that the median of the “exacerbation-free time” of the reference treatment is 2 months, and therefore, the “non-inferiority” condition requires that the median in the experimental group be similar. It is considered appropriate to set a “noninferiority” limit of 0.60 units in multiplicative terms with respect to the reference treatment; In other words, an attempt will be made to demonstrate that the experimental treatment provides at least a median of the exacerbation-free time of not less than 1.2 months (36 days), if it is exacerbated before this period of time the study didn't comply the “non inferiority” condition. Thus, we calculated that a minimum sample of 58 patients per treatment group (in total 116) was required to ensure a power of 80% and a significance level of 5%. Exacerbation-free time was defined as the interval between discharge from the home and the moment of exacerbation, until the end of the study when it did not occur or in the event of loss of follow-up until the last recorded time. All analyzes were performed according to the principle of intention to treat.

The statistical analysis of the main variable was carried out using the Kaplan-Meier method and the statistical test of the log-rank test.

The comparison between the two groups was made with the Student t test for continuous variables and the non-parametric Mann-Whitney test when the normality test was rejected.

The statistical package used was Stata V.15.1.

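### The plan gives two non-inferiority limits, a 0.60 ratio to control and a fixed 36-day experimental median; they agree only if the control median is 60 days, and only the 36-day version carries a written failure condition

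*Combined protocol and SAP*

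**What the plan says.** All the wording at issue is in the Statistic analysis section of the combined protocol and SAP.

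- **Hypothesis.** Results under the intervention "are not inferior to the reference treatment (control") arm. This is a comparison between randomised groups.
- **Relative limit.** The investigators "set a “noninferiority” limit of 0.60 units in multiplicative terms with respect to the reference treatment".
- **Planning value.** From the literature, the median exacerbation-free time "of the reference treatment is 2 months".
- **Absolute restatement.** A connecting phrase then turns the limit into a requirement on the experimental arm alone: that it "provides at least a median of the exacerbation-free time of not less than 1.2 months (36 days), if it is exacerbated before this period of" (the sentence runs on into the failure condition).
- **Failure condition.** The only pass/fail wording in the plan is tied to that period: "if it is exacerbated before this period of time the study didn't comply the" non-inferiority condition. I read its subject as the experimental median, the only quantity the sentence has introduced.
- **Sample size.** 58 per group, 116 in total, for 80% power at a 5% level whose sidedness is not stated.
- **Primary analysis.** Kaplan-Meier curves and a log-rank test. No confidence interval for a ratio is mentioned, and the 0.60 limit does not reappear.

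**The concern.** A limit stated as a ratio moves with the control arm of the trial; a limit stated as 36 days does not. The plan treats them as the same thing, but the 36 days contains no quantity estimated from the randomised controls.

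The stake is the primary conclusion. If controls stay exacerbation-free for longer than two months, an experimental arm whose median is less than 0.60 of its control's can still clear 36 days. If controls exacerbate sooner, an experimental arm that equals its control can miss 36 days. Two analysts following the same text could report opposite conclusions from the same data, one using the ratio and the other the day count.

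A confidence bound on the experimental median alone would not cure this, because the bound would still be set against 36 days.

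**Working it through.** **Inputs from the plan.** Limit 0.60; assumed control median 2 months (60 days); 58 per arm; 5% level; 80% power. Follow-up of 6 months (180 days) is read from the visit schedule under Comparative interventions. **Assumptions of mine.** Exponential times, no dropout, and every control median other than 60 days; the latter are illustrative and not in the documents.

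**1. The plan's own figures reproduce.**

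- Threshold: 0.60 × 60 = 36 days.
- Events (Freedman, one-sided 5%, 80% power): (1.645 + 0.842)² × [(1 + 0.60)/(1 − 0.60)]² = 6.18 × 16 = 98.9, so 99.
- Event probability by 6 months: 1 − 0.5^(6/2) = 0.875.
- Patients: 99/0.875 = 113.1, so 114, against 116 stated.
- Two-sided 5% needs 126 events and 126/0.875 = 144 patients, which does not match.

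The sample size is therefore consistent with a two-arm ratio comparison at a one-sided 5% level.

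**2. Where the two limits part.**

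| Control median (days) | 0.60 × control (days) | Ratio implied by 36 days |
|---|---|---|
| 30 | 18 | 1.20 |
| 45 | 27 | 0.80 |
| 60 | 36 | 0.60 |
| 90 | 54 | 0.40 |
| 120 | 72 | 0.30 |

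**3. The 36-day rule read literally.** With 58 patients and no censoring before day 36, the Kaplan-Meier median is the 29th ordered time. The rule passes when at most 28 patients have had an event before day 36. For a true experimental median m, the pass probability is P[Bin(58, p) ≤ 28] with p = 1 − 0.5^(36/m).

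| Control / experimental (days) | True ratio | p | Passes 36-day rule |
|---|---|---|---|
| 120 / 60 | 0.50 | 0.340 | 0.99 |
| 90 / 45 | 0.50 | 0.426 | 0.84 |
| 30 / 30 | 1.00 | 0.565 | 0.13 |

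With the true ratio exactly at 0.60, the rule passes about 1%, 45%, 84%, 97% and more than 99% of trials at control medians of 40, 60, 75, 90 and 120 days. It has no fixed error rate at the limit.

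**4. A ratio rule on the same data.** Pass if ln(HR) + 1.645 × √(1/d_E + 1/d_C) < ln(1/0.60), where HR is the experimental/control hazard ratio and d_E and d_C are the event counts in the two arms. By simulation with 180-day censoring:

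- 120/60 and 90/45: under 1% pass.
- At the limit (60/36 and 120/72): about 5% pass.
- Equal arms: 86% pass at 30/30, 82% at 60/60 and 71% at 120/120.

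The error at the limit stays near 5% whatever the control median. Power falls somewhat when events are slower.

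**The case against.** **The 36 days may be only an illustration.** It is introduced as a rewording of the ratio and sits between the literature median and the sample-size sentence, and 116 patients follows from a ratio calculation. A reader might infer that the plan definitely adopts a fixed 36-day rule; the text does not settle that. What remains is that the sole failure condition names the 36-day period, and nothing ties that period to the observed control median.

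**The control arm is in the analysis.** A reader might infer that the controls play no part in the decision. That goes too far, because the log-rank test compares the randomised arms. Under the assumptions above it would be significant at two-sided 5% in roughly nine trials in ten at 120/60 and 90/45. Requiring both a 36-day median and no significant log-rank disadvantage would pass only about 7% to 10% of those trials. But the plan does not write that combined rule, and a non-significant log-rank result is not a test against 0.60. Nor would an added condition help the 30/30 case, since it can only lower the 13%.

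**The plan may intend inference rather than a bare observed median.** It speaks of demonstrating the limit at a 5% level. A one-sided 95% lower limit for the experimental median can be taken as the 23rd ordered time, so the pass probability becomes P[Bin(58, p) ≤ 22]. This gives about 28% at 90/45 and 78% at 120/60. The problem shrinks in the first case and stays large in the second.

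**A control median away from 60 days is not shown.** Entry excludes patients who "have required ICU care or need mechanical ventilation non-invasive during exacerbation", and the clock starts at discharge from home care. A reader might infer that the control median must therefore differ from two months. The documents do not describe the population or time origin behind the literature figure, so this is possible but not established. Near 60 days the two limits almost coincide.

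**Conclusion.** The point stands as an inconsistency in the decision threshold. The plan states a relative limit and an absolute one that are equivalent only at a 60-day control median, attaches its failure condition to the absolute one, and lists no analysis that applies the ratio.

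The error could be large in either direction: a 99% pass rate at a true ratio of 0.50 (120/60), and 13% when the arms are equal at 30 days. Those sizes rest on exponential times, 58 per arm, a literal reading of the rule on the observed median, and control medians that I assumed. They show what the wording permits, not what happened in this trial.

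The sample size is not at fault on this point. It reproduces to within two patients from a one-sided 5% ratio calculation, which suggests that the ratio was the intended limit. The wording should be settled before the primary conclusion is drawn or reported.

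**What to change.** In the Statistic analysis section:

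1. Label 36 days (1.2 months) as a planning illustration at an assumed 60-day control median, and remove it as the pass/fail criterion.
2. State that non-inferiority is concluded only if the one-sided 95% confidence limit for the experimental/control ratio, with both arms estimated in this trial, excludes 0.60. For example, the upper limit of the hazard ratio should lie below 1/0.60 = 1.67. A hazard ratio translates into a ratio of medians in this way under proportional hazards with exponential times, and that assumption should be written down.
3. State the sidedness of the 5%. One-sided 5% is the level that reproduces about 116 patients. If two-sided 5% was meant, 116 × 0.875 = 101.5 expected events give about 73% power.
4. Report the observed control median beside the assumed 60 days.

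Make this change together with any repair of the missing margin-based test, since one sentence can serve both. The cost is a few sentences, with no new data and, at the 60-day planning value with a one-sided 5% level, no change in sample size. Because the document describes the trial as already carried out, the change should be dated and reported as a clarification.

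### The 0.60 non-inferiority limit and the 80% power belong to a hazard-ratio test that the plan does not contain; the log-rank test it names cannot show non-inferiority

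*Combined protocol and SAP*

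**What the plan says.** All of the relevant text but one sentence is in the Statistic analysis section of the combined protocol and SAP.

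- **Hypothesis.** After early discharge, results with telemonitoring are to be shown not inferior to those of the control group.
- **Limit.** The literature median "of the reference treatment is 2 months", and the margin is a "limit of 0.60 units in multiplicative terms with respect to the reference treatment". This is restated as a "median of the exacerbation-free time of not less than 1.2 months (36 days") in the experimental group.
- **Size.** At least 58 per group, 116 in total, was "required to ensure a power of 80% and a significance level of 5" per cent. The text gives no sidedness, effect measure, formula, expected number of events or allowance for loss.
- **Primary analysis.** It was "carried out using the Kaplan-Meier method and the statistical test of the log-rank test". The section mentions no hazard ratio and no confidence interval.

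The Protocol section adds: "Substitution of patients withdrawn from the study was not performed".

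**The concern.** A non-inferiority claim needs an analysis that sets the result, with its uncertainty, against the margin. The plan defines a margin and sizes the trial for it, then names a test whose null hypothesis is that the two curves are the same. That test can reject equality. It cannot show that telemonitoring is no worse than the limit.

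Two things are at stake. First, the natural misuse is to report a non-significant log-rank p-value as proof of non-inferiority, which carries a much larger risk of a false claim than the stated 5%. Second, because sidedness is not stated, a later analyst could set either a 90% or a 95% interval against the limit, and the conclusion could turn on that choice.

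**Working it through.** **Inputs from the plan.** Control median 2 months; limit 0.60; 58 per group; power 80%; level 5%, sides not stated.

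**Assumptions.** Exponential times, so that a median ratio of 0.60 is a hazard ratio of 1/0.60 = 1.67; arms truly equal when computing non-inferiority power; follow-up of 6 months per patient. The last is taken from the visit schedule under Comparative interventions; the plan itself censors at the end of the study.

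**1. Reproducing the plan's figure (one-sided 5%).**
- Probability of an event by 6 months: 1 − 2^(−6/2) = 0.875. Expected events: 116 × 0.875 = 101.5.
- Events needed (Schoenfeld): 4(1.645 + 0.842)² / (ln 1.667)² = 4 × 6.183 / 0.2609 = 94.8, so 95.
- Power: Φ(√101.5 × 0.5108/2 − 1.645) = Φ(0.928) = 82.3%.
- Freedman's formula: (1.6/0.4)² × 6.183 = 98.9, so 99 events; 99/0.875 = 113.1, or 114 patients in equal arms against the stated 116. Power at 116 is Φ(√101.5 × 0.25 − 1.645) = 80.9%.
- Simulation (10,000 trials, Cox model): 81.4%.

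The size therefore reproduces approximately as a one-sided 5% non-inferiority test on the hazard-ratio scale.

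**2. The same test at two-sided 5%.** Φ(√101.5 × 0.5108/2 − 1.960) = Φ(0.613) = 73.0%; simulated 72.4%.

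**3. What the named log-rank test does when the true ratio is at the limit.**
- Control event probability 0.875; experimental (median 1.2 months) 1 − 2^(−6/1.2) = 0.969; average 0.922. Events: 116 × 0.922 = 106.9.
- Chance of significance at two-sided 5%: Φ(√106.9 × 0.5108/2 − 1.960) = Φ(0.681) = 75.2%; simulated 75.2%. Non-significant: about 25%.
- At one-sided 5% the chance of significance is about 84%, so it is non-significant about 16% of the time.

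Reading non-significance as non-inferiority would thus give a false claim at the limit in about 25% (or 16%) of trials, against 5% for a proper one-sided 5% test.

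**4. Where the two rules disagree.** With 101.5 events the standard error of the log hazard ratio is about 2/√101.5 = 0.199.
- Two-sided 5% log-rank non-significant on the harmful side: observed hazard ratio below exp(1.960 × 0.1985) = 1.48.
- Upper 90% limit below 1.67: observed hazard ratio below exp(0.5108 − 1.645 × 0.1985) = 1.20.

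An observed hazard ratio between about 1.20 and 1.48 would be non-significant and yet fail to show non-inferiority.

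**5. Effect of loss on the one-sided power (10% lost).**
- Losses spread evenly over 6 months: a lost patient has event probability 1 − 0.875/(6 × 0.3466) = 0.58. Events: 116 × (0.9 × 0.875 + 0.1 × 0.579) = 98.1; power 81.2%.
- Lost patients contribute no events: 101.5 × 0.9 = 91.4 events; power 78.7%.

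**The case against.** The best argument for the plan is that the sample size is sound. The hypothesis is directional and the margin is on a ratio scale, so a one-sided level and a ratio test are the natural reading, and that reading returns about 80%. This stands: the point is not an error in the 116.

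It may also be said that the limit is used, because the Kaplan-Meier median of the experimental group can be set against 36 days. That gives a descriptive criterion only. No confidence limit is attached, so neither the 5% nor the 80% applies to it. A fixed 36 days also equals 0.60 of control only if the control median turns out to be 2 months.

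A reader might infer more than the documents support:

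- **That the trial has only 73–75% power.** Those figures come from a two-sided level, which the plan never states. At one-sided 5% the log-rank test has 82–84% power to detect a ratio at the limit. Power to detect a difference is, besides, a different quantity from power to show non-inferiority.
- **That power is about 60% because the limit is worded in medians.** That figure belongs to a formal test of the ratio of Kaplan-Meier medians, which the plan does not name.
- **That power drops below 80% once about 7% are lost.** This assumes that lost patients contribute no events, whereas the plan counts them to their last recorded time. With losses spread evenly, the Schoenfeld power crosses 80% at about 20% loss.
- **That no two-sided reading comes near 80%.** If all 116 patients had an event, two-sided 5% power would be about 79%. That reading needs 122 patients and no censoring, so it fits the stated size less well than the one-sided reading.

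**Conclusion.** The point holds as a mismatch between hypothesis and test, not as a shortfall in sample size. The analysis for which the trial was evidently sized, a one-sided 5% comparison of the hazard ratio with 1.67, is absent. The test that is present cannot support the stated aim: at the limit itself it would be non-significant about 25% of the time at two-sided 5%. The missing sidedness matters because it moves the power of the non-inferiority test between about 81–82% and about 73%.

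The power figures depend on exponential times, a 2-month control median and 6-month follow-up. The mismatch depends on none of these.

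**What to change.** Amend the Statistic analysis section as follows.

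1. State that the 5% level is one-sided.
2. Make this the primary decision: non-inferiority is concluded if the upper limit of the two-sided 90% confidence interval for the hazard ratio (intervention versus control, Cox model) is below 1.67. State that 1.67 is 1/0.60 and relies on exponential times.
3. State the 95 events required and power of about 81–82% at full 6-month follow-up. Add that power falls with loss: on the Schoenfeld figure, at 10% loss, to about 81% if losses are spread evenly and 79% if lost patients contribute no events.
4. Keep the log-rank test as supportive and the comparison of medians as descriptive, and say that a non-significant log-rank result does not establish non-inferiority.

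The Protocol section describes the trial as carried out to July 2018. The text should therefore record when this rule was fixed, and that it follows from the sample-size calculation rather than from the results.

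The cost is one extra model and some wording. No enlargement is needed.

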The secondary variables analyzed were: the use of healthcare resources measured as the number of home visits by healthcare personnel (scheduled and unscheduled), average time hospitalized at home, exacerbations after discharge and readmissions for this reason. Other secondary variables: 1) degree of satisfaction with home care (Satisfad questionnaire¹⁰) and for the intervention group also a specific survey, consisting of four questions with answers using a five-level Likert scale (assessment from 1 to 5, from lower to greater satisfaction and / or need for help) and a fifth open-ended question about their experience with the monitor. 2) Measurement of anxiety and depression using the STAI questionnaire (trait-trend) in the home hospitalization phase. 3) Impact on well-being and quality of life using the CAT (COPD Assessment Test) questionnaire. 4) Therapeutic compliance through the Morinsky-Green-Levine questionnaire at the beginning and at the sixth month; additionally for the intervention group, adherence to telemonitoring was determined based on compliance with the protocolized shipments.

Comparative interventions:

The first phase of the study was hospitalization at home (with or without telemonitoring depending on the assigned group) and the second phase was follow-up after medical discharge (identical for both groups, without telemonitoring); with one consultation a month and another at 6 months. In these consultations, outpatient and / or hospital exacerbations were collected, as well as other study variables.

Control group (conventional home hospitalization):

** Visiting regime: a first visit is made in the hospital (doctor and nurse who will follow up), making a clinical evaluation and management of the bronchodilators.

The rest of the visits are daily at home and will initially be carried out only by the infirmary, except for the final visit in which the doctor accompanies him to discharge the patient, if he meets the following criteria:

- Clinical stability, with recovery from daily activities, with dyspnea similar to its baseline.
- Saturation levels > 90% with or without oxygen and lower requirements for short acting adrenergic beta2 agonists.
- Correct use of medication.

Constants are taken, physical examination, clinical evaluation and health education (involving knowledge of your disease, inhalation technique, therapeutic compliance, exercise respiratory, nutritional advice and smoking cessation if needed).

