Intervention group (Home Hospitalization with Telemedicine):

** Regimen of home visits: 1) An initial visit to the hospital (doctor and nurse), 2) an intermediate visit by the nurse, 3) the last visit :discharged the patient by the nurse and the doctor. The nursing actions in the visits, the hours of attention and the discharge criteria are the same as those detailed in the control group. On the first day that the patient was at home, he received a visit from the technician, who installed the telemonitoring equipment and trained the patient and family members in its handling (leaving them a contact telephone number for incidents).

** Telemonitoring: to carry it out, a multi-parameter recording equipment with communication capacity over the GSM network was used, which sent the data to an online web platform, which was reviewed by the responsible doctor.

The parameters recorded were: ECG (leads I, II, III), O2 Saturation (%), heart rate, blood pressure, temperature and respiratory rate.

The patient sent them twice a day (morning and afternoon), at approximately the same time (weekdays), and later received a phone call from the doctor to assess their clinical situation (symptoms, degree of dyspnea (mMRC), changes in appearance and amount of sputum, compliance and complications) and decide the action to follow.

Thresholds of normal intervals were established in the before mentioned parameters, outside these ranges, a warning was generated in the form of sms

to the medical phone. If an intervention was necessary, they contacted the patient and explained the action plan (home visit, going to the emergency room, changing medication, etc.).

Statistic analysis:

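### Intention to treat is the only analysis set for a non-inferiority claim, so the result cannot show whether telemonitoring matched daily visits or was only partly delivered

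*Combined protocol and SAP*

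**What the plan says.** Under Statistic analysis, the main hypothesis is that the results of the intervention "are not inferior to the reference treatment (control)". The plan chooses to "set a “noninferiority” limit of 0.60 units in multiplicative terms with respect to the reference treatment". It takes from the literature that "the median of the “exacerbation-free time” of the reference treatment is 2 months", so the limit corresponds to "a median of the exacerbation-free time of not less than 1.2 months (36 days)". The sample is 58 per group, chosen "to ensure a power of 80% and a significance level of 5"%, with sidedness not stated. The primary analysis is Kaplan-Meier with a log-rank test. On populations there is a single sentence: "All analyzes were performed according to the principle of intention to treat". No per-protocol set, as-treated set or adherence-based sensitivity analysis is defined.

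Four other statements bear on the point:

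- Study variables: in the intervention group, "adherence to telemonitoring was determined based on compliance with the protocolized shipments". Scheduled and unscheduled home visits are also counted.
- Withdrawal criteria: inability to use telemonitoring is a reason for withdrawal, and withdrawn patients are not replaced.
- Intervention group: there is one intermediate nurse visit between the hospital visit and the discharge visit, where control has daily visits. After an out-of-range reading, "If an intervention was necessary, they contacted the patient and explained the action plan", and a home visit is one of the listed actions.
- Statistic analysis: exacerbation-free time starts at discharge from home hospitalization, after telemonitoring has ended.

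**The concern.** In a superiority trial, keeping non-users in their assigned arm usually makes a positive claim harder. In a non-inferiority trial the protection can reverse. If intervention patients who did not use the monitor have outcomes like those of control, the observed ratio moves towards 1 and away from 0.60, and incomplete delivery helps the claim.

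The two arms differ only in the short home phase, because later follow-up is the same for both and has no telemonitoring. Incomplete delivery in that phase therefore acts on the whole contrast. A finding of non-inferiority could mean that telemonitoring does as well as daily visits, or that too few patients were monitored for a difference to show. Intention to treat alone cannot separate the two, and the plan gives no use to the data that would help.

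**Working it through.** **Inputs from the documents.** 58 per arm; control median 2 months; limit 0.60; level 5%; power 80%; last scheduled consultation at 6 months.

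**Assumptions.** Exponential times; follow-up to 6 months; one-sided testing; non-inferiority declared when the upper confidence limit for the hazard ratio is below the margin. The plan describes no such limit, only a log-rank test, so this rule is supplied for the check.

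**Margin.** 0.60 × 2 = 1.2 months. With exponential times the hazard-ratio margin is 1/0.60 = 1.667, and ln(1.667) = 0.511.

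**The plan's sample size.** Freedman's formula, one-sided 5%, 80% power: events = [(1.645 + 0.842) × (1 + 0.6)/(1 − 0.6)]² = (2.487 × 4)² ≈ 99. The event probability by 6 months at a median of 2 months is 1 − 0.5^(6/2) = 0.875. Then 99/0.875 = 113.1, or 57 per arm, close to the stated 58. The two-sided version needs 126 events, or 126/0.875 = 144 patients, and does not match. One-sided 5% is therefore the working level.

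**Simulated false non-inferiority.** Monitor users are placed exactly at the limit (median 1.2 months), so a claim of non-inferiority for users is false. A random share of the intervention arm are non-users. The documents give no share, so 10 to 30% is an assumed range.

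| Non-users | ITT, non-users like control | ITT, non-users worse (median ratio 0.4) | Per-protocol, non-users like control |
|---|---|---|---|
| 0% | about 5% | about 5% | about 5% |
| 10% | about 9% | about 3.5% | about 5% |
| 20% | about 15% | about 2.3% | about 5% |
| 30% | about 22% | about 1.6% | about 5% |

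At one-sided 2.5%, the first ITT column becomes about 2.6%, 5%, 9% and 14%.

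**Hand check of the first ITT column.** Expected events are 58 × 0.875 = 50.75 in control and, for users, 58 × (1 − 0.5^(6/1.2)) = 58 × 0.969 = 56.2. The standard error of the log hazard ratio is √(1/50.75 + 1/56.2) = 0.194. If a share c of non-users shrinks the log hazard ratio to (1 − c) × 0.511, the claim rate is Φ(c × 0.511/0.194 − 1.645):

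- c = 0.1: Φ(0.26 − 1.645) ≈ 8%
- c = 0.2: Φ(0.53 − 1.645) ≈ 13%
- c = 0.3: Φ(0.79 − 1.645) ≈ 20%

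The simulation runs slightly higher because users exacerbate sooner, so those still at risk are increasingly non-users.

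**Cost of requiring both analyses.** When the arms are truly equal, power is about 82% with no exclusions. Requiring both analyses to meet the limit gives about 79%, 76% and 73% at 10, 20 and 30% exclusion. Repeated simulation runs differ by up to about one percentage point.

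**The case against.** The strongest case against has four parts.

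*No fall-back is described.* A reader might infer that patients who abandon the monitor return to daily visits and so pull the arms together. The documents do not support that. Inability to use the equipment is a withdrawal criterion, and no transfer to daily visits is mentioned. A low user who stays in the arm keeps the reduced visit schedule and so has neither full monitoring nor daily visits. Such patients could do worse than control, and the error then falls below 5%. This stands: the direction of bias is open.

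*Home visits after an alert are part of the intervention.* The action plan lists them, so they are not contamination. This stands too.

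*The simulated test is not the plan's.* The plan sets no confidence limit against 0.60. Patients withdrawn during the home phase leave before the endpoint's time origin, and how intention to treat counts them is undefined. This stands, and it adds two items to the fix.

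*Per-protocol is no safeguard in itself.* It holds near 5% in the table because non-use was assumed to be unrelated to prognosis. Suppose instead that users and non-users alike are at the limit, 20% of each arm are frail with twice the hazard, and the frail are excluded from the intervention arm only. Per-protocol error is then about 14%, against about 6% for intention to treat, and requiring both gives about 6%. So per-protocol must not replace intention to treat, and its set must not be shaped by deterioration. Requiring both, however, can never give a higher false-claim rate than intention to treat alone.

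Eligibility rules and technician training may also keep non-use low, but the documents give no rate.

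**Conclusion.** The gap is real: the plan makes a non-inferiority claim on a single analysis set, with adherence recorded but unused. What it does to the error rate is conditional. If non-users resemble control, 10 to 30% non-use takes the false non-inferiority rate from 5% to between about 9% and 22%. If they do worse, at an assumed median ratio of 0.4, it drops to between about 3.5% and 1.6%. Both ranges rest on exponential times, 6 months of follow-up, one-sided 5%, an assumed margin test, users exactly at the limit and non-use at random.

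It would be tempting to conclude that poor delivery necessarily favours the trial's claim. That needs a non-use rate and a description of the care non-users receive, and the documents give neither. Confidence is high that the second analysis is missing, and low on the size and direction of the bias. The change is a worthwhile, inexpensive improvement; the documents do not show that the trial's conclusion is invalid.

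**What to change.** Keep intention to treat and make these changes:

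1. Add a pre-specified per-protocol analysis of exacerbation-free time. For both analyses, give a confidence interval for the ratio against the same 0.60 limit, and state its level and sidedness.
2. Define the per-protocol set in advance. In the intervention arm, use a minimum share of the scheduled transmissions sent while the patient was in the home phase (75% would be one example; the trial team must set the figure). In control, use receipt of the scheduled visits.
3. Do not count alert-triggered home visits as deviations, and do not exclude patients because they deteriorated or were readmitted.
4. Base the non-inferiority claim on agreement of the two analyses, and discuss any disagreement.
5. Report departures from assigned care by arm, with reasons.
6. State how patients withdrawn before discharge from home, and so before time zero, are counted in intention to treat.

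The cost is some analysis-plan text and a second run of the same model on data already collected. The per-protocol set is smaller and open to selection, and the joint requirement takes the power loss shown in the working.
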